 initiation of any other anticancer therapy.
- 4. Follow up visit required only for subjects who terminated treatment for reasons other than death or disease progression.
- 5. Information on subject's survival and use of subsequent anticancer therapy may be collected by phone. Upon disease progression, all subjects will be followed approximately every 12 weeks for survival and the use of subsequent therapy until either death or 12 months after accrual in the subject's study cohort has been completed, whichever occurs first.
- Medical history is to include demographics, primary diagnosis and WHO classification, outcome and duration of response to prior cancer therapy and any ongoing AEs
- 7. At the screening visit, record the number of RBC, whole blood and platelet transfusions for the four months prior to Cycle 1 Day 1; for all other visits, the number of transfusions should be recorded since the last study visit.
- Assessed from date of first signature of ICF, throughout the course of treatment and approximately 30 days after treatment discontinuation. Additional assessments may be performed until AE resolution or the AE is deemed irreversible by the Investigator.
- 9. Assessment is to be performed within 14 days prior to the first administration of study drug.
- If not collected within the 14 days prior to Cycle 1 Day 1, record subject's weight and vital signs prior to dosing on Cycle 1
 Day 1 only.
- 11. Assessment is to be performed within 72 hours prior to first administration of study drug on Day 1 of Cycle 1.
- 12. To be performed in women with childbearing potential only
- 13. Assessment is to be performed beginning on Cycle 2 Day 1 and Day 1 of every cycle thereafter.
- 14. Fasting for laboratory testing is not required. Laboratory tests may be conducted on additional time points if deemed necessary by the Investigator. Samples will be analyzed locally at the clinical site or its reference laboratory. Laboratory assessments may be repeated if values are borderline to inclusion level or may change due to best supportive care measures. Hematology should include: hemoglobin, reticulocytes, platelets, WBCs, neutrophils, neutrophil precursors (promyelocytes, myelocytes, metamyelocytes, band neutrophils), monocytes, lymphocytes and blasts. Serum chemistry should include: AST, ALT, total bilirubin, creatinine, BUN, potassium and calcium. Coagulation should include: PT/INR, APTT.

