9.4 Dose Selection

This study will evaluate two dose regimens: 600 mg administered bid on Days 1-7 of 28 day treatment cycles with the possibility to dose escalate to 800 mg bid, or to dose reduce to 400 or 200 mg bid, and 300 mg administered bid on Days 1-21 of 28 day treatment cycles with the possibility to dose reduce to 200 or 100 mg bid in order to support optimal dose selection for further clinical studies in subjects with MDS who are RBC transfusion dependent.

In the majority of its phase 2 program, tipifarnib was given orally at a dose of 300 mg bid for 21 days, followed by 1 week of rest, in 28 day treatment cycles (3 weeks on/1 week off schedule). Prior studies have shown that

those shown to demonstrate anti-tumor activity in preclinical tumor models. In a multicenter, phase 2 study in higher risk MDS patients (INT-28, N = 82), in which tipifarnib 300 mg bid was administered on the 3 weeks on/1 week off schedule, the response rate (CR + CRp + PR) was 15.9% and did not meet prespecified criteria (30% in order to reject null hypothesis) to support continued development in MDS using 300 mg bid 3 weeks on/1 week off. The most frequently reported hematologic AEs were thrombocytopenia (41%), anemia (34%), and granulocytopenia (29%). The most frequently reported non-hematologic AEs were fatigue (51%), diarrhea (38%), nausea (37%), and rash (24%). The observed safety profile in MDS patients was broadly similar to the other patient populations in which tipifarnib has been tested. For further details, please refer to the Investigator's Brochure.

However, given the underlying cytopenias often observed in patients with MDS, consideration was made for exploring alternative regimens that have been associated with less myelosuppression. The effect of higher dose levels given at intermittent schedules was tested in several clinical studies, including two trials in MDS and AML patients investigating alternate week dosing (7-day bid dosing followed by 7-day rest).

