6. ANALYSIS POPULATIONS

Full Analysis Set (FAS)

The full analysis set (FAS) will serve as the primary population for the analysis of ORR and other efficacy-related data. Prior to Protocol Amendment 3 (version 09 Jul 2017), other subjects were enrolled into the trial using a different dose regimen. Also, for inclusion in the FAS, subjects must meet all Protocol Amendment 3 inclusion criteria. For the purposes of the primary analysis (advancement from stage 1 to stage 2 and overall analysis for each dose regimen

cohort), those subjects will not be included. The excluded subject data will be summarized separately in the reporting of the study.

Therefore, subjects will be excluded for FAS for the following reasons:

- Did not meet eligibility criteria as outlined in Protocol Amendment 3 (version 09 Jul 2017)
- Failure to receive at least one dose of tipifarnib
- No post-baseline endpoint data subsequent to at least 1 dose of study drug.
- Enrolled prior to Protocol Amendment 3 (version 09 Jul 2017)

Per-Protocol (PP) Population

A supportive analysis may be performed on the PP population which excludes subjects due to important deviations from the protocol that may substantially affect the results of the primary analysis, such as not taking at least 80% of the intended dose in cycle 1. The final determination on protocol violations, and thereby the composition of the PP population, will be made prior to locking the clinical database and final analysis and will be documented in a separate memorandum.

All Subjects as Treated (ASaT) Population

The ASaT population will be used for the analysis of safety data. The ASaT population consists of all enrolled subjects who receive at least one dose of tipifarnib. At least one laboratory or vital sign measurement obtained subsequent to at least one dose of study drug is required for inclusion in the analysis of a specific safety parameter. To assess change from baseline, a baseline measurement is also required.

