9.2. Secondary Efficacy Analyses

Transfusion independence and disease response will be summarized descriptively per dose regimen cohort and overall.

The duration of objective response will be calculated for subjects who achieve CR, PR, marrow CR or HI. For such subjects, the duration of objective response is defined as the number of days from the start date of response (whichever response is achieved first) to the first date that progressive disease(PD) is objectively documented. Disease progression will be determined by the Investigator using MDS IWG criteria (Table 9 in the study protocol). The DOR will be right-censored for subjects who achieve a response and meet 1 of the following conditions:

- 1) Non-protocol anticancer treatment started before documentation of disease progression;
- 2) Death or documented disease progression after more than 1 missed disease assessment visit;
- 3) Alive and does not have documentation of disease progression before a data analysis cutoff date.

The DOR will be summarized descriptively using the Kaplan-Meier method. The 50th percentile of the Kaplan-Meier distribution will be used to estimate the median response duration.

PFS will be defined as the time (in months) from enrollment to either first observation of progressive disease or occurrence of death due to any cause within 1 year (approximately 4 time intervals for disease assessments) of either first administration of tipifarnib or the last disease assessment. Similarly, survival will be defined as the time (in months) from enrollment to occurrence of death due to any cause within 1 year (approximately 4 time intervals for disease assessments) of either first administration of tipifarnib or the last disease assessment.

Determination of RBC transfusion independence will be assessed by the Investigator through the review of subject transfusion requirements and hemoglobin levels. RBC TI will be defined as the absence of the intravenous infusion of any RBC transfusion during any consecutive “rolling” 56 days during the treatment period, i.e. days 1 to 56, days 2 to 57, days 3 to 58, etc. and a ≥ 1 g/dL increase in hemoglobin level. The rise in the hemoglobin concentration in subjects who no longer require transfusions will be calculated as the difference between the maximum hemoglobin concentration and the minimum pre-transfusion value during the 12 weeks before enrollment in the study.

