13. DATA HANDLING CONVENTIONS

Analyses will be performed using SAS® [SAS Institute 2011] Version 9.3 or higher.

The clinical database will be locked prior to the initiation of the Stage 1 statistical analyses. A database lock is defined as a stable database that can be analyzed and reported. Changes to a locked database must be authorized in writing by the study sponsor [REDACTED]

The data conventions include the following.

- Data will be described and summarized by study stage (Stage 1 or Stage 2), Stage 1 cohort (starting dose level and schedule), or Stage 2 cohort (disease type).
- Summary tables for continuous variables will contain the following statistics: N (number of subjects in the population); n (number of subjects with data for that variable); mean; standard deviation; median; minimum; and maximum. Selected statistics may also include 2 sided 95% normal approximation confidence intervals (CI) on the mean.
- Summary tables for categorical variables will include: N (number of subjects in the denominator); n (number of subjects in the numerator); and percent. Selected statistics also may include 2-sided 95% CIs for the percent, calculated using the CL=AGRESTICOULL option in SAS PROC FREQ.

- The baseline value for a given parameter is the last value prior to the first dose. A value is considered to be post-baseline if it is obtained after the first dose. A value is considered to be postdose on a given cycle day if it is obtained after the dose is administered on that day.
- Data from all study centers will be pooled for all analyses.
- Unless otherwise specified, statistical testing will be 2-sided at a nominal 0.05 level of significance.
- Study day is defined as calendar date – date of first treatment + 1 if the calendar date is on or after the date of first treatment, and calendar date – date of first treatment if the calendar date is before the date of first treatment
- Measurements from unscheduled visits will be included in listings, but not summary tables.
- Missing data conventions for individual endpoints are described in the SAP section for the endpoint.
- Additional exploratory analyses may be performed as deemed appropriate after review of the pre-specified analyses. Log-transformations or nonparametric tests may be applied to measurements displaying a significant degree of non-normality.
- Listings will be provided for all data collected in the eCRF.

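### The RBC transfusion independence rate has no baseline transfusion requirement, so never-transfused subjects enter it and can bias it in either direction

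*SAP*

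**What the plan says.** SAP 9.2 (repeated in Protocol 12.2.1; Protocol 10.1 has the definition without the hemoglobin calculation) gives RBC TI two limbs, both required.

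- **Transfusion limb.** "RBC TI will be defined as the absence of the intravenous infusion of any RBC transfusion during any consecutive" rolling 56-day window during treatment.
- **Hemoglobin limb.** A "1 g/dL increase in hemoglobin level" or more. The reference is given for one group only: "The rise in the hemoglobin concentration in subjects who no longer require transfusions will be calculated as" the maximum hemoglobin minus the lowest pre-transfusion value in the 12 weeks before enrollment.

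On who is counted, SAP 6 says "The full analysis set (FAS) will serve as the primary population for the analysis of ORR and other efficacy-related data". SAP 9.2 says "Transfusion independence and disease response will be summarized descriptively per dose regimen cohort and overall". No TI-evaluable subset is defined, and SAP 7.4 plans no subgroup analyses. None of the 11 inclusion criteria in Protocol 7.1 concerns hemoglobin or transfusion dependence; criterion 7 covers neutrophils and platelets only.

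Baseline transfusion history is collected: Protocol Table 1, footnote 7, tells sites to "record the number of RBC, whole blood and platelet transfusions for the four months prior to Cycle 1 Day 1". Neither document uses it to decide who can be assessed for TI.

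**The concern.** A TI rate is meant to show how many subjects who needed red cells stopped needing them. Here a subject who never needed red cells is in the denominator and satisfies the transfusion limb without any change in condition, given 56 days on treatment. Whether that subject then counts as a success rests on a hemoglobin calculation that the plan does not define for such a subject.

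Rate and duration of TI are the first two items listed under Secondary Objective 1. Protocol 9.4 describes the regimens as supporting dose selection for "further clinical studies in subjects with MDS who are RBC transfusion dependent". A rate that blends dependent and never-dependent subjects does not describe that group. With 11 to 18 subjects per cohort, a chance imbalance in baseline transfusion status could also look like a difference between regimens.

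**Working it through.** **1. The plan's own figures.** The documents state no expected TI rate. The only figures labelled RBC TI are the design figures in SAP 5 and the matching protocol section, so these were checked first.

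- Stopping after stage 1 is P(X ≤ 1 of 11). At 10%: 0.9^11 + 11 × 0.1 × 0.9^10 = 0.3138 + 0.3835 = 0.697. At 30%: 0.7^11 + 11 × 0.3 × 0.7^10 = 0.0198 + 0.0932 = 0.113. Both match.
- Declaring a cohort of interest is the sum over k ≥ 2 of P(X1 = k) × P(X2 ≥ 4 − k), with X1 from 11 subjects and X2 from 7. This gives 0.0875 at 10% (stated 0.087) and 0.8001 at 30% (stated 80%). Both match.

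These figures do not depend on how TI is defined.

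**2. A never-transfused subject under the written rule.**

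- Denominator: included, since the population is the FAS and nothing restricts it.
- Transfusion limb: met by default.
- Hemoglobin limb: no pre-transfusion value exists, so the stated calculation cannot be done.

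Three readings are then open to a programmer:

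- (a) Fall back on the general convention in SAP 13, "The baseline value for a given parameter is the last value prior to the first dose", so that the subject can count as TI.
- (b) Treat the limb as not met, leaving a failure in the denominator.
- (c) Treat the value as missing and drop the subject under SAP 7.5, which uses reduced denominators for missing data points.

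Assumed example: 18 subjects, 9 untransfused at baseline; 1 of the 9 transfused subjects becomes independent; 4 of the 9 untransfused show the rise against their last pre-dose value. The same data give (a) 5/18 = 28%, (b) 1/18 = 6%, (c) 1/9 = 11%. Only (c) is a rate among transfused subjects.

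**3. Size over a range.** Let f be the share untransfused at baseline, t the TI rate in transfused subjects, and q the share of untransfused subjects counted as TI. The documents give none of these, so all are assumptions.

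Reported FAS rate = (1 − f) × t + f × q. With t = 10%:

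| f | q = 0 | q = 0.3 | q = 0.5 |
|---|---|---|---|
| 1/3 | 6.7% | 16.7% | 23.3% |
| 1/2 | 5.0% | 20.0% | 30.0% |
| 2/3 | 3.3% | 23.3% | 36.7% |

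Example: f = 2/3, q = 0.5 gives 0.333 × 0.10 + 0.667 × 0.5 = 0.367. With t = 30% and f = 1/2, the row is 15%, 30%, 40%. The error is upward when q > t, downward when q < t, and zero when they are equal.

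**4. How large q could be with no drug effect under reading (a).** A simulation assumed independent hemoglobin values, a within-subject SD of 0.3 to 0.7 g/dL and a single baseline value. The best of 3 on-treatment values exceeded baseline by at least 1 g/dL in 2.4% to 31.6% of subjects; with 7 values, in 4.7% to 47.1%. Taking the extremes with f = 1/2 and t = 10%: 0.05 + 0.5 × 0.024 = 6.2%, and 0.05 + 0.5 × 0.471 = 28.6%. The hemoglobin limb therefore limits false counting but does not exclude it.

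**The case against.** The strongest reply is that the hemoglobin rule speaks only of subjects who have stopped needing transfusions, so a never-transfused subject cannot be scored as TI at all, and the missing-data rule would remove that subject. Part of this stands. A reader might infer that the written rule necessarily counts never-transfused subjects as successes and so inflates the rate. The documents do not support that: the transfusion limb alone is not enough, and the hemoglobin limb has no stated reference for these subjects. The reply does not cure the problem, however. The wording sits in the calculation of the rise and does not restrict the denominator. SAP 7.5 concerns data points that are missing, and does not clearly reach a value that could never exist.

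Impact is also limited. TI is summarized descriptively, and no between-regimen test of TI is planned. SAP 8.3 summarizes prior transfusions and SAP 10.3 lists transfusions, so a careful reader could see who had been transfused. Protocol 9.4 closes by stating the dose-selection aim for MDS generally, so it goes too far to say that the TI rate is useless for dose selection.

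Because the sample-size text and table label the 10% versus 30% rates as RBC TI, a reader might also infer that the go/no-go decision is affected. It is not: Protocol 12.2.1 bases stage 2 advancement and the overall outcome on ORR.

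The IWG tables (Protocol Tables 9 and 10) were not in the available text. They are cited for response and progression, whereas RBC TI has its own definition.

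**Conclusion.** The concern holds as a gap in the endpoint definition. Following the plan puts never-transfused subjects into the TI rate and leaves one of its two limbs undefined for them, so the result does not measure becoming transfusion independent. The direction of the error is not fixed. Over the assumed ranges (one third to two thirds untransfused, 0% to 50% of them counted), a true 10% reads as 3.3% to 36.7%. These inputs are illustrative and do not come from the documents. TI duration inherits the same gap. The consequence is confined to a listed but descriptive secondary endpoint; it should be corrected, and it does not disturb the primary analysis.

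**What to change.** In SAP 9.2 and Protocol 12.2.1 (with 10.1 aligned), define a TI-evaluable set: FAS subjects with at least one RBC transfusion in the 12 weeks before enrollment. Use it as the denominator for TI rate and as the source population for TI duration. Twelve weeks is the window the plan already uses for the hemoglobin reference, so both limbs can be computed for everyone in the denominator, provided the pre-transfusion hemoglobin that the existing rule presupposes is available. Report hemoglobin change in the remaining FAS subjects separately, and not as TI.

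**Cost.** A few sentences in each document. The four-month history covers the window if enrollment falls within the 28-day screening period: 12 × 7 + 28 = 112 days. The schedule asks for the number of transfusions, however, so applying the window needs their dates. Protocol 14.2 already requires dates in the subject file, but they may have to be retrieved from there. The denominator shrinks and the interval widens: if 6, 9 or 12 of 18 subjects are untransfused, 12, 9 or 6 remain, and one subject is worth 8.3, 11.1 or 16.7 percentage points instead of 5.6.

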9.3. Exploratory Efficacy Analyses

Biomarker analysis will be managed and analyzed by Kura Oncology, Inc and will not be a part of this statistical analysis plan. Details will be described elsewhere.

10. SAFETY ANALYSES

Safety and tolerability of tipifarnib will be assessed based on the following:

- Incidence, duration and severity of TEAEs, SAEs, AEs resulting in permanent discontinuation of study drug, and deaths within approximately 30 days from the last dose of study drug (or immediately before the administration of another anti-cancer treatment)
- Changes in laboratory test results
- Serum Chemistry: Blood Urea Nitrogen, Creatinine, Potassium, Calcium, Total Bilirubin, ALT, AST
- Hematology: White Blood Cell Count, Hemoglobin, Platelet Count, Absolute Neutrophil Count, Neutrophil Precursors (promyelocytes, myelocytes, metamyelocytes, band neutrophils), Lymphocytes, Monocytes, Blasts, and Reticulocytes.
- Coagulation panel: PT/INR, APTT
- Changes in vital signs: blood pressure, heart rate, temperature

Unless explicitly indicated otherwise, all analyses for safety will be based on the ASaT population.

10.1. Adverse Events

Adverse events will be coded using the latest available version of the Medical Dictionary for Regulatory Activities (MedDRA). Treatment-emergent adverse events are defined as AEs that start on or after the first dose of study drug and within approximately 30 days of the last administration of study drug. AEs will be summarized by the number and percentage of subjects who experienced the event, according to SOC and PT. A subject reporting multiple cases of the same AE will be counted once within each SOC and similarly counted once within each PT. For summaries by maximum severity, each subject will be counted only once under the most severe event.

Unless specified otherwise, the denominator for these calculations will be based on the number of subjects who received at least one administration of tipifarnib regardless of the total number of doses or treatment cycles administered. These conventions will be appropriately modified to calculate AE incidence rates separately for each cycle that study therapy is administered. AE incidence rates may also be calculated based on other measures of subject exposure (e.g., total number of treatment cycles administered). For subjects enrolled prior to Protocol Amendment 3, their AE counts will only be provided in the Total column (Regimen 1 + Regimen 2 + Original Cohort). Regimen 1 and Regimen 2 subjects will be presented separately and in the Total columns.

AE durations will be calculated using all TEAEs. For any AE that is still ongoing at the end of study, we will use the last contact date as the end of AE stop date for calculation the duration of AEs. Median, minimum and maximum of AE durations will be reported.

AEs will also be summarized by NCI-CTCAE version 4.03 severity grade and by relationship to each study drug. Additional summaries may also be provided for SAEs, and events resulting in the permanent discontinuation of therapy. All AEs will be included in individual subject listings.

Hematologic abnormalities reported as AEs that were coded to preferred terms in the Investigations SOC have been pooled with appropriate terms in the Blood and Lymphatic System SOC for tabulation for the following categories:

- Platelet count decreased = Thrombocytopenia;
- Neutrophil count decreased = Neutropenia;
- White blood cell count decreased = Leukopenia;
- Lymphocyte count decreased = Lymphopenia.

Overall view of TEAEs will be provided, which will include the total number of TEAEs, frequency of subjects with TEAEs, drug-related AEs, SAEs, drug-related SAEs, or death within 30-days within administration of study-drug; and AEs leading to permanent discontinuation of study drug. Additionally, a corresponding overall view of exposure-adjusted AE incidence will be provided, in which the exposure-adjusted incidence rate, is calculated as the mean number of events per treatment cycle, with corresponding 95% confidence intervals.

Summary tables will be provided which present the incidence of TEAEs by SOC and PT; and the incidence of TEAEs by SOC/PT by maximum severity (NCI-CTCAE Grades 1 through 5).

Summary tables will be provided which present the incidence of hematology-related TEAEs by SOC and PT; and the incidence of hematology-related TEAEs by SOC/PT by maximum toxicity grade.

A summary of the AE durations for all TEAEs by SOC/PT will be provided.

Summary tables will be provided which present the incidence of study-drug related TEAEs; and the incidence of study-drug related TEAEs severity scores of Grade 3 or higher.

Summary tables will be provided which present the incidence of SAEs by SOC/PT; and the incidence of TEAEs leading to permanent discontinuation of drug by SOC/PT.

Data on AEs will be presented in listings.

